3.1 Statistical Hypotheses

Sequential hypotheses testing with Bonferroni-based multiplicity control over the overall Type I error rate at 5% for 2-sided tests and 2.5% for 1-sided tests for the co-primary endpoints and then the co-secondary/secondary endpoints will be performed in order as defined in each supplemental cohort. The margins of 1-sided non-inferiority tests on the neutralizing antibody titers to the COVID-19 variant of interest in the study intervention group are a 1.5-fold rise in geometric mean titers (GMTs) and -10% for seroresponse rates, compared to that in the comparator group. The margin of 1-sided superiority tests on the post-booster neutralizing antibody titers to the COVID-19 variant of interest in the study intervention group is a 2-fold rise in GMT compared to pre-booster.

3.1.1 Evaluation of Booster candidates in Supplemental Cohorts 1 and 2

For Supplemental Cohorts 1 and 2 in younger adults (18-55 years of age), 3 booster candidates in total: CoV2 preS dTM-AS03 (D614) in Supplemental Cohort 1 and CoV2 preS dTM-AS03 (B.1.351) and CoV2 preS dTM-AS03 (D614 + B.1.351) in Supplemental Cohort 2, share the same Comparator Group of SARS-CoV-2-naïve adults, unvaccinated, 18-55 years of age, who will receive the CoV2 preS dTM-AS03 (D614) vaccine as a primary series of 2 injections given 21 days apart, for hypothesis testing. To control for multiple testing, the Bonferroni adjustment will be applied to maintain overall type I error at 0.025 one-sided (0.025/3 for each comparison of booster candidate).

[figure not shown]

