For the CoV2 preS dTM-AS03 (D614) booster candidate, there are 2 co-primary endpoints to be hypotheses tested with one-sided alpha 0.025/3 in participants primed with the Pfizer/BioNTech vaccine. If the primary objectives are met, then 2 conditional secondary endpoints will be hypotheses tested with one-sided alpha 0.025/3 applying the sequential testing strategy in participants primed with the CoV2 preS dTM-AS03 (D614) vaccine in the Original Phase II Cohort. If the primary objectives in the Pfizer/BioNTech vaccine primed and conditional secondary objectives in the CoV2 preS dTM-AS03 (D614) vaccine primed are both met, then 2 conditional secondary endpoints will be hypotheses tested with one-sided alpha 0.025/3 applying the sequential testing strategy in participants primed with an mRNA vaccine. If the primary objectives in the Pfizer/BioNTech vaccine primed, conditional secondary objectives in the CoV2 preS dTM-AS03 (D614) vaccine primed, and conditional secondary objectives in the mRNA vaccine primed are all met, then 2 conditional secondary endpoints will be hypotheses tested with

one-sided alpha 0.025/3 applying the sequential testing strategy in participants primed with an adenovirus vector vaccine. If the primary objectives in the Pfizer/BioNTech vaccine primed and conditional secondary objectives in the CoV2 preS dTM-AS03 (D614) vaccine primed, the mRNA vaccine primed, and adenovirus vector vaccine primed are all met, then 1 conditional secondary endpoint on seroresponse will be hypotheses tested at one-sided alpha 0.025/3 in each Pfizer/BioNTech primed, CoV2 preS dTM-AS03 (D614) primed, mRNA primed, and adenovirus vector primed sequentially by applying the sequential testing strategy.

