Conditional secondary objective 4: non-inferiority in terms of seroresponse rate for participants primed with the Pfizer/BioNTech, CoV2 preS dTM-AS03 (D614), mRNA, or adenovirus vector vaccines:

For participants, 18-55 years old, primed with the Pfizer/BioNTech vaccine, the CoV2 preS dTM-AS03 (D614) vaccine, an mRNA vaccine, or an adenovirus vector vaccine, 14 days after the booster dose (ie, D15) with CoV2 preS dTM-AS03 (D614) and 14 days after the second dose (ie, D36) of the Comparator Group, the seroresponse rate against D614G of the Booster Group CoV2 preS dTM-AS03 (D614), is non-inferior to the seroresponse rate against D614G of the Comparator Group.

Null hypothesis (H_0) : $p_{(booster)} - p_{(comparator)} \leq -10\%$

Alternative hypothesis (H_1) : $p_{(booster)} - p_{(comparator)} > -10\%$

The Pfizer/BioNTech vaccine primed, CoV2 preS dTM-AS03 (D614) vaccine primed, mRNA vaccine primed, and adenovirus vector vaccine primed will be tested sequentially. The non-

inferiority will be demonstrated if the lower limit of the two-sided 98.3% CI of the difference between the 2 proportions is greater than -10%.

3.1.1.3 Supplemental Cohort 2

For CoV2 preS dTM-AS03 (B.1.351) (non-exploratory arm only), hypothesis testing will be conducted for the 2 co-primary immunogenicity endpoints in participants, 18-55 years of age, primed with the Pfizer/BioNTech vaccine, 2 conditional co-secondary immunogenicity endpoints in participants, 18-55 years of age, primed with an mRNA vaccine, 1 conditional secondary endpoint on GMT in participants, 18-55 years of age, primed with the Pfizer/BioNTech vaccine, 1 conditional secondary endpoint on seroresponse in participants, 18-55 years of age, primed with the Pfizer/BioNTech vaccine and an mRNA vaccine sequentially.

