3.2 Sample Size Determination

3.2.1 Supplemental Phase III Cohorts 1 and 2

A Bonferroni adjustment is used to control the overall type I error rate at 0.025 one-sided in Supplemental Cohorts 1 and 2, so each comparison of the Booster Group with the Comparator Group will be performed at one-sided significance level of 0.00833 (0.025/3). No alpha-splitting within hypothesis testing of co-primary endpoints. Assumed attrition rate of Primary Vaccination Group is 10% and Booster Group is 3% (it is anticipated that attrition to 14 days post booster will be limited and smaller than the attrition to D36 in the Comparator Group). Other assumptions for sample size calculation are as follows:

- The PsVN Std Dev is around 0.65 for primary vaccination at D36 and around 1.0 for booster vaccination at D22 on \log_{10} scale base on immunogenicity data obtained from Monogram for the corresponding assay
 - Note: The assumption of the standard deviation of the assay is based on the final interim data of D614G on the PPAS Naïve-D01+D22 at D36 and FAS NonNaïveD01 at D22 from VAT0002 Original Phase II Cohort in participants 18-55 years of age.
- For the primary and secondary objectives in terms of GMT non-inferiority against the comparator (using the D614G titers elicited by the comparator as the benchmark), the ratio of group GMT margin is 1/1.5, the assumed true ratio of group GMT for D614 containing vaccines (comparing D614G titers in both booster vaccine and priming comparator) is 1.5 (this is informed by preliminary interim data from VAT0002 Original Phase II Cohort, indicating titers generally higher in the non-naïve individuals after a single dose, compared to the titers in naïve individuals after 2 doses); and the assumed true ratio of group GMT for the B1.351 variant-containing vaccines (comparing B.1.351 titers in variant-containing vaccines versus D614G titers in the comparator D614 vaccine) is 1 (this is assumed in the absence of data).

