3.4.4 Secondary Endpoints - Immunogenicity

For Supplemental Cohorts 1 and 2 conditional secondary objectives on non-inferiority claim of post-booster versus post-primary vaccination, the statistical inference will be based on the use of the two-sided 98.3% CI of difference in geometric means of post-vaccination \log_{10} transformed titer values between the 2 groups with normal approximation.

The margin used for non-inferiority hypothesis testing are $1/1.5=0.667$ for GMTs. The non-inferiority in terms of GMTs will be demonstrated if the lower limit of the 2-sided 98.3% CI (Supplemental Cohorts 1 and 2) for the difference of \log_{10} (GMT) of tested vaccine candidate arm and \log_{10} (GMT) of the control arm $> \log_{10}(1/1.5)$.

For Supplemental Cohorts 1 and 2 conditional secondary objectives on superiority claim of post-booster versus pre-booster, the two-sided 98.3% CI of post-booster versus pre-booster will be calculated using \log_{10} -transformed titers assuming a normal distribution.

The margin used for superiority hypothesis testing on post-booster versus pre-booster responses in Supplemental Cohorts 1 and 2 on individual group GMTRs is 2. The superiority in terms of GMTRs will be demonstrated if the lower limit of the 2-sided 98.3% CI (Supplemental Cohorts 1 and 2) of \log_{10} (GMTRs) $> \log_{10}(2)$.

For Supplemental Cohort 2 conditional secondary objective on superiority claim of B.1.351 for post-booster versus post-primary vaccination, the two-sided 98.3% CI of post-booster versus post-primary will be based on the use of the two-sided 98.3% CI of difference in geometric means of post-vaccination \log_{10} transformed titer values between the 2 groups with normal approximation.

The margin used for superiority hypothesis testing on post-booster versus post-primary responses to B.1.351 in Supplemental Cohort 2 on individual group GMTRs is 1.5. The superiority in terms

of GMTRs will be demonstrated, if the lower limit of the 2-sided 98.3% CI (Supplemental Cohorts 1 and 2) of $\log_{10}(\text{GMTRs}) > \log_{10}(1.5)$.

For Supplemental Cohorts 1 and 2 conditional secondary objectives on non-inferiority claim of seroresponse, the two-sided 98.3% CI difference in proportions between groups will be computed using the Wilson score method without continuity correction.

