The margin used for non-inferiority hypothesis testing is -10% for seroresponse rate. The non-inferiority in terms of seroresponse rates will be demonstrated if the lower limit of the 2-sided 98.3% CI for the difference of seroresponse rates > -0.1 .

Confidence interval for the difference in proportions between two groups

For the non-inferiority hypotheses in terms of seroresponse rate, the two-sided 95% CI difference in proportions between groups will be computed using the Wilson score method without continuity correction (2) as follows:

Let $\hat{\theta} = \pi_A - \pi_B$, then if $L = \hat{\theta} - \delta$ and $U = \hat{\theta} + \varepsilon$ are respectively the lower and the upper limits of the CI, where:

$$\delta = Z_{\alpha/2} \sqrt{\left\{ \frac{l_1(1-l_1)}{n_1} + \frac{u_2(1-u_2)}{n_2} \right\}}$$

$$\varepsilon = Z_{\alpha/2} \sqrt{\left\{ \frac{l_2(1-l_2)}{n_2} + \frac{u_1(1-u_1)}{n_1} \right\}}$$

l_1 and u_1 are calculated from the CI of the single proportion in Group A given by:

$$\frac{(2n_1 p_1 + Z_{\alpha/2}^2 \pm Z_{\alpha/2} \sqrt{(Z_{\alpha/2}^2 + 4n_1 p_1(1-p_1))})}{2(n_1 + Z_{\alpha/2}^2)}$$

l_2 and u_2 are calculated from the CI of the single proportion in Group B given by:

$$\frac{(2n_2 p_2 + Z_{\alpha/2}^2 \pm Z_{\alpha/2} \sqrt{(Z_{\alpha/2}^2 + 4n_2 p_2(1-p_2))})}{2(n_2 + Z_{\alpha/2}^2)}$$

where $Z_{\alpha/2}$ is the upper $(1-\alpha/2)$ th percentile of the standard normal distribution.

The margin used for non-inferiority hypothesis testing is -10% for seroresponse rate. The non-inferiority in terms of seroresponse rates will be demonstrated if the lower limit of the 2-sided 95% CI for the difference of seroresponse rates > -0.1 .

The percentage of responders and participants having 2-fold rise (2FR), 4-fold rise (4FR) will be provided against each endpoint with the corresponding 95% CIs using the Clopper-Pearson method. FR defined as fold-rise from post-vaccination relative to pre-vaccination, the pre-vaccination could be the D01 at Phase III study or D01 at Phase II study for CoV2 preS dTM-

AS03 primed participants. Differences of percentages of responders and participants with 2FR, 4FR will be provided with 95% CI calculated by Newcombe-Wilson score method without continuity correction.

Confidence interval for the single proportion

The exact 2-sided 95% CI for the single proportion will be constructed using Clopper-Pearson's method, quoted by Newcombe where:

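### SAP Section 3.4.4 states the seroresponse non-inferiority rule with both a 98.3% and a 95% confidence interval; the 95% version triples the allotted alpha

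*SAP*

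**What the plan says.** Section 3.1.1 splits the error rate over three booster candidates that share one comparator: "the Bonferroni adjustment will be applied to maintain overall type I error at 0.025 one-sided (0.025/3 for each comparison of booster candidate"). The seroresponse step is inside that allocation. For the Cohort 1 candidate, "1 conditional secondary endpoint on seroresponse will be hypotheses tested at one-sided alpha 0.025/3", and the two Cohort 2 candidates are treated the same way.

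The hypothesis sections carry this through. Section 3.1.1.2 requires the "lower limit of the two-sided 98.3% CI of the difference between the 2 proportions is greater than -10" percent, and Section 3.1.1.3 repeats the rule for Cohort 2. Section 3.2.1 sizes each comparison at a "one-sided significance level of 0.00833 (0.025/3"), and every seroresponse row of Table 3.1 shows a type I error of 0.00833.

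Section 3.4.4 then states the analysis twice:

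- First, for the seroresponse non-inferiority claim, "the two-sided 98.3% CI difference in proportions between groups will be computed using the Wilson score method without continuity correction", followed by a decision rule on that 98.3% interval with margin -0.1.
- Then, under the subheading on the interval for a difference in proportions: "For the non-inferiority hypotheses in terms of seroresponse rate, the two-sided 95% CI difference in proportions between groups will be computed". After the formulas, the same margin is applied to a different interval: non-inferiority "will be demonstrated if the lower limit of the 2-sided 95% CI for the difference of seroresponse rates > -0.1".

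The formula block uses a generic Z at alpha/2 and gives no value for alpha.

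**The concern.** The same hypotheses, margin and interval method have two success criteria that cannot both apply. The 95% lines cannot be read as descriptive output: they name the non-inferiority hypotheses and end in a pass/fail rule. The descriptive 95% intervals for differences in responders and fold-rises come in a separate paragraph afterwards. Section 5, on changes to planned analyses, does not resolve the conflict.

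Under the 95% rule each seroresponse hypothesis is tested at one-sided 0.025, so the overall 0.025 across three candidates is no longer protected at this step. If the two statements are noticed only after unblinding, choosing between them amounts to choosing alpha with the data in view.

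There is a smaller related point. The figure 98.3% is itself rounded; taken literally it corresponds to one-sided 0.0085, not 0.00833.

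**Working it through.** **Inputs from the SAP.** Margin -10%; assumed true rates 96.5% (booster) and 99% (comparator); attrition 3% (booster) and 10% (comparator), all in Section 3.2.1. Comparator N=515, so 463 evaluable. Booster N=215, 270, 290 and 150 in Cohort 1 (208, 261, 281 and 145 evaluable), and 515 and 590 in Cohort 2 (499 and 572 evaluable), from Table 3.1. Evaluable numbers are rounded down.

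**Nominal levels.**
- Allotted: 0.025/3 = 0.00833 one-sided, i.e. a two-sided level of 1 - 0.05/3 = 98.33%, Z = 2.394.
- 95% rule: 0.05/2 = 0.025 one-sided, Z = 1.960. Ratio 0.025/0.00833 = 3.
- 98.3% taken literally: (1 - 0.983)/2 = 0.0085, Z = 2.387; 3 × 0.0085 = 0.0255.

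**Interval.** Section 3.4.4 gives the lower limit as

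L = p₁ - p₂ - Z √[ l₁(1-l₁)/n₁ + u₂(1-u₂)/n₂ ],

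where l₁ is the Wilson lower limit for the booster group and u₂ the Wilson upper limit for the comparator. Non-inferiority is shown if L > -0.10. Power and type I error below come from summing exact binomial probabilities over all outcomes that satisfy this rule.

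**Step 1: reproduce Table 3.1 (96.5% vs 99%).**

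| Booster N | Stated power | At 0.025/3 | At 0.025 (95% CI) |
|---|---|---|---|
| 215 | 95.3% | 95.1% | 98.8% |
| 270 | 98.9% | 98.6% | 99.7% |
| 290 | 99.4% | 99.2% | 99.9% |
| 150 | 78.2% | 78.8% | 92.7% |

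The table is reproduced within one percentage point at 0.025/3. At 0.025 the N=150 row is more than 14 points too high.

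**Step 2: type I error at the margin (89% vs 99%).**

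| Booster N | At 0.025/3 | 95% rule |
|---|---|---|
| 150 | 0.0045 | 0.0196 |
| 215 | 0.0057 | 0.0215 |
| 290 | 0.0059 | 0.0225 |
| 515 | 0.0076 | 0.0240 |
| 590 | 0.0080 | 0.0262 |

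Under the 95% rule the error is about 3 to 4 times larger, and above 0.00833 in every row.

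**Step 3: three candidates together.** The Bonferroni bound is 3 × 0.025 = 0.075, against 3 × 0.00833 = 0.025. Allowing for the shared comparator, and taking the Pfizer-primed groups (208, 499 and 499 evaluable) all exactly at the margin on one strain each, the exact chance of at least one false claim is 0.067 under the 95% rule and 0.0207 at 0.025/3.

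**Step 4: does the verdict change?** Take 458/463 comparator responders (98.9%) and 137/145 adenovirus-primed responders (94.5%), a difference of -0.0444.
- 95%: l₁ = 0.8949, u₂ = 0.9954; the subtracted term is 0.0503; L = -0.0947, pass.
- 98.33%: l₁ = 0.8803, u₂ = 0.9961; the subtracted term is 0.0649; L = -0.1093, fail.

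At 138/145, L is -0.0859 (95%, pass) and -0.1002 (98.33%, fail). At least 137 responders are needed at 95% and 139 at 98.33%. For the Cohort 1 Pfizer-primed group (208 evaluable) the thresholds are 194 and 196.

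**Rounding.** At 138/145 a literal 98.3% gives L = -0.09997, a pass, where 98.33% fails. The N=150 error rate moves from 0.0045 to 0.0053; for N=215 it is 0.0057 either way.

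**The case against.** The strongest reply is that the intended level is not in doubt. Every hypothesis statement, the first half of Section 3.4.4 and Table 3.1 point to 0.025/3, so the 95% lines look like leftover wording and a careful programmer would use 98.3%. That is probably how the conflict arose, but it does not remove it. A confirmatory success criterion should not have to be inferred, and the only level stated next to the formula is 95%.

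The reach is also limited, and this stands:

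- Seroresponse comes last in each candidate's sequence: after eight GMT tests in four priming groups in Cohort 1, and after the primary, mRNA-primed and B.1.351 superiority steps in Cohort 2. No primary objective or GMT claim is affected.
- The inflation bites only when the earlier steps have been passed and the seroresponse null is true. Control of the overall error rate must still hold in that case.
- The 0.075 is an upper bound; the exact worst case computed above is 0.067.
- Cohort 2 power exceeds 99.9% under either rule, and in the two worked examples the verdict changes over only two participants.
- The calculations assume 463 comparators, while Section 3.1.1.1 foresees a shortfall. With 260 they are similar: 0.0060 vs 0.0218 for N=215, and 0.0054 vs 0.0203 for N=150.

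The rounding of 98.3% is fairly called minor. It is arithmetically right and worth correcting in the same edit, but would not justify an amendment by itself.

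**Conclusion.** The concern holds and must be fixed. Two statements in Section 3.4.4, the interval level and the decision rule beneath the formula, contradict the 98.3% rule in the same section, the hypothesis sections and the alpha allocation. As written, the 95% rule permits testing at three times the allotted nominal alpha, with exact error rates at the margin of about 0.020 to 0.026 where 0.00833 is allowed.

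The Table 3.1 power figures identify the 95% wording as the mistake. The practical effect is largest for the adenovirus-primed group (power 78.8% against 92.7%).

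These figures rest on the SAP's assumed rates and attrition, on 463 evaluable comparators, and, for type I error, on a true comparator rate of 99% with the booster group exactly 10 points lower.

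**What to change.** In Section 3.4.4, in the passage on the interval for the difference in proportions, replace both 95% statements tied to the seroresponse non-inferiority hypotheses with the two-sided 100(1-0.05/3)% interval. State that Z is taken at one-sided 0.025/3 (about 2.394). Keep 95% only for the differences in responders and fold-rises that are reported descriptively.

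In the same edit, define the confirmatory level once as 100(1-0.05/3)% (98.33%), or as a one-sided test at 0.025/3, and let 98.3% elsewhere refer to that definition.

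The cost is SAP wording and one macro parameter. Design, sample size, data collection and Table 3.1 are unchanged.

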Study intervention groups and assignment method	
Participants will be screened for eligibility criteria at the time of inclusion.
 
 Supplemental Cohort 1: previously vaccinated participants will be stratified based on the priming vaccine received 4 to \leq 10 months prior and by age group (18-55 years of age and 56 years of age and older) and will receive a single booster dose of CoV2 preS dTM-AS03 (D614). Supplemental Cohort 2, Main Arms: Participants previously vaccinated with an authorized/approved mRNA or adenovirus-vectored COVID-19 vaccine will be stratified based on the vaccine received 4 to \leq 10 months prior and by age group (18-55 years of age and 56 years of age and older) and randomly assigned to 1 of the following booster formulations in a 1:1 ratio: 
 CoV2 preS dTM-AS03 (B.1.351) CoV2 preS dTM-AS03 (D614 + B.1.351) Participants previously vaccinated with CoV2 preS dTM-AS03 (D614) as a primary series in the Original Phase II Cohort will be stratified by age group (18-55 years of age and 56 years of age and older) and randomly assigned to 1 of the following booster formulations in a 9:1 ratio for younger adults (D614:B.1.351) and a 1:1 ratio for older adults: 
 CoV2 preS dTM-AS03 (D614) CoV2 preS dTM-AS03 (B.1.351) Supplemental Cohort 2 Exploratory B.1.351 Arms: participants previously vaccinated with the Pfizer/BioNTech mRNA vaccine

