	
• Primed with J&J/Janssen:
○ 18-55 years of age: 75 participants○ 56 years of age and older: 25 participants
	
Supplemental Cohort 2, Main Arms: adults vaccinated 4 to \leq 10 months prior will be stratified by primary vaccine and by age and randomized to receive 1 of the following as a single booster dose:
 
• Primed with Pfizer/BioNTech:
○ CoV2 preS dTM (D614 + B.1.351):
■ 18-55 years of age: 515 participants■ 56 years of age and older: 50 participants○ CoV2 preS dTM (B.1.351):
■ 18-55 years of age: 515 participants■ 56 years of age and older: 50 participants• Primed with CoV2 preS dTM-AS03 (actual numbers will depend on eligibility and consent for Cohort 2 participation of participants enrolled in the Original Phase II Cohort; numbers below are estimates and subject to change):
○ CoV2 preS dTM-AS03 (B.1.351):
■ 18-55 years of age: 30 participants■ 56 years of age and older: 75 participants○ CoV2 preS dTM-AS03 (D614):
■ 18-55 years of age: 270 participants■ 56 years of age and older: 75 participants• Primed with Moderna:
○ CoV2 preS dTM-AS03 (D614 + B.1.351):
■ 18-55 years of age: 75 participants■ 56 years of age and older: 25 participants○ CoV2 preS dTM-AS03 (B.1.351):
■ 18-55 years of age: 75 participants■ 56 years of age and older: 25 participants• Primed with Oxford University/AstraZeneca:
○ CoV2 preS dTM-AS03 (D614 + B.1.351):
■ 18-55 years of age: 75 participants■ 56 years of age and older: 25 participants○ CoV2 preS dTM-AS03 (B.1.351):
■ 18-55 years of age: 75 participants■ 56 years of age and older: 25 participants• Primed with J&J/Janssen:
○ CoV2 preS dTM-AS03 (D614 + B.1.351):
■ 18-55 years of age: 75 participants■ 56 years of age and older: 25 participants

	
○ CoV2 preS dTM-AS03 (B.1.351):
▪ 18-55 years of age: 75 participants▪ 56 years of age and older: 25 participants

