The Geometric mean of titer ratio is defined as:

$$GMTR = \left(\prod_{i=1}^n ratio_i \right)^{\frac{1}{n}} = 10^{\frac{\sum_{i=1}^n \log_{10}(ratio_i)}{n}} = 10^{\frac{\sum_{i=1}^n \log_{10}\left(\frac{post_i}{pre_i}\right)}{n}}$$

The normal approximation will be used to calculate the 2-sided 98.3% CIs for the individual group GMTRs as follows:

$$10^{(\bar{x} \pm t_{n-1, \alpha/2} \sqrt{v(\bar{x})})}$$

where $10^{(\bar{x})}$ is the GMTR, $\bar{x} = \frac{1}{N} \sum \log_{10}(x)$, $\log_{10}(x)$ is the log base 10 of the titer ratio (post/pre), N is the number of subjects with non-missing value for pre and post-vaccination,

$\sqrt{V(\bar{x})}$ is the estimated standard deviation of \bar{x} , and $t_{n-1, \alpha/2}$ is the 100(1- $\alpha/2$) percentile of the central t -distribution with $n-1$ degrees of freedom.

The margin used for superiority hypothesis testing are 2 for individual group GMTRs. The superiority in terms of GMTRs will be demonstrated if the lower limit of the 2-sided 98.3% CI (Supplemental Cohorts 1 and 2) for the mean of \log_{10} (GMTRs) $> \log_{10}(2)$.

GMTs in each injection group and GMT ratios between injection groups will be descriptively summarized along with their 95% CIs using the normal approximation of log-transformed titers. GMTs will be presented in original scale that are re-converted from log-transformed titers. The 95% CI of GMT ratios between booster arms and comparator group will base on the Welch's t-interval for Supplemental Cohort 1 and 2 will base on the Student t-distribution.

Analyses will be performed for both FAS and PPAS, but the conclusion will be made mainly from results based on PPAS and supported by results based on FAS.

Subgroup analyses, where applicable, will be performed by age-group (18-55 years and ≥ 56 years) for intervention groups, by priming vaccine (Supplemental Cohorts 1 and 2), and by priming platform (Supplemental Cohorts 1 and 2), in addition to the Overall group.

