Lower bound: $1 - Beta(1 - \alpha / 2, n - r + 1, r)$ and

Upper bound: $Beta(1 - \alpha / 2, r + 1, n - r)$

where r is the observed number of events/responders in n observations.

GMTs or GMCs in each injection group and GMT or GMC ratios between injection groups will be descriptively summarized along with their 95% CIs using the normal approximation of log-transformed titers. GMTs or GMCs will be presented in original scale that are re-converted from log-transformed titers. The 95% CI of GMT or GMC ratios between booster arms and comparator group will base on the Welch's t-interval for Supplemental Cohort 1 and 2.

The 95% CI of GMT ratios after booster dose at D15 between booster arms based on the Student t-distribution and 95% CI of difference on seroresponse rate at D15 relative to D01 between booster arms based on the Newcombe-Wilson score method without continuity correction will be provided for homogeneity/comparability evaluation on booster effect across different primary series vaccines, by age group and overall.

GMTRs or GMCRs is defined as ratio of individual geometric mean titer or concentration for each injection group (post-vaccination/pre-vaccination for each injection). GMTR or GMCR will be summarized with 95% CI (Normal approximation). Additional parameters may be displayed as appropriate.

Confidence interval for the individual group GMT or GMC and GMTR or GMCR

The normal approximation will be used to calculate the 2-sided 95% CIs for the individual group GMT or GMC and GMTRs or GMCRs as follows:

$$10^{(\bar{x} \pm t_{n-1, \alpha/2} \sqrt{v(\bar{x})})}$$

where $10^{(\bar{x})}$ is the GMT or GMC, $\bar{x} = \frac{1}{N} \sum \log_{10}(x)$, $\log_{10}(x)$ is the log base 10 of the observed titer or concentration, N is the total observation in each injection group, $\sqrt{V(\bar{x})}$ is the estimated standard deviation of \bar{x} , and $t_{n-1, \alpha/2}$ is the 100(1- $\alpha/2$) percentile of the central t -distribution with $n-1$ degrees of freedom.

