4.3 Complementary Assessment of External Samples/Data

External blood samples/data from different sources will be analyzed as complementary analysis to further assess the immunogenicity profile of study vaccine.

The external blood samples/data from different sources will be analyzed separately by sample repository and combined as one per the primary series vaccine.

The sample selected from external sources are from adults, ≥ 18 years of age. As the samples are de-identified, other demographic and baseline characteristics are not available. The time point of blood samples are based on time interval of pre-vaccination and post-vaccination matched with the VAT00002 study time intervals as closely as possible. The external data is considered as belong to naïve participants before COVID-19 vaccination, however, no exact match to the study definition could be applied, for example, the participants are presumed to be naïve to SARS-CoV-2 base on antibody levels.

The Monogram assay will be used to evaluate immune responses in the blood samples.

GMTs in each and combined sample repository, and GMT ratios between external data group and booster arm will be descriptively summarized along with their 95% CIs using the normal approximation of log-transformed titers. GMTs will be presented in original scale that are re-converted from log-transformed titers. The 95% CI of GMT ratios between groups will be based on the Welch's t-interval for primary series vaccination group and booster arm, the 95% CI of GMT ratios between primary series vaccination groups will be based on the Student t-distribution.

GMTR or GMCR will be summarized with 95% CI (Normal approximation).

Estimated seroresponse will be calculated by post dose versus pre dose with antibody titer. Additional parameters may be displayed as appropriate.

5 Changes in the Conduct of the Trial or Planned Analyses

- A pooled primary series cohort as Supplemental Cohorts 2 Comparator Group**

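### Descriptive GMT-ratio intervals between booster arms, and between external primary-series groups, are assigned the Student t-distribution where the Welch interval already in the SAP would be safer (minor)

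*SAP*

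**What the plan says.** The SAP uses two interval methods for ratios of geometric means between independent groups.

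- **Booster arm versus Comparator.** Section 3.4.2 prints the Welch formula with its approximate degrees of freedom and applies it to the 98.3% inferential intervals. Section 3.4.4 keeps Welch for the descriptive 95% intervals: "ratios between booster arms and comparator group will base on the Welch's t-interval".
- **Booster arm versus booster arm at D15.** Section 3.4.4 specifies "The 95% CI of GMT ratios after booster dose at D15 between booster arms based on the Student t-distribution". The stated use is "homogeneity/comparability evaluation on booster effect across different primary series vaccines, by age group and overall".
- **External samples.** Section 4.3 uses Welch for a primary-series group against a booster arm, but "the 95% CI of GMT ratios between primary series vaccination groups will be based on the Student t-distribution".
- **Descriptive paragraph of 3.4.2.** One sentence about booster versus Comparator names Welch and then runs on with "for Supplemental Cohort 1 and 2 will base on the Student t-distribution". Part of the sentence seems to have been lost.

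The SAP does not write out the variance estimator behind the Student intervals.

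**The concern.** Welch's interval is itself a t-interval. When a plan names Welch for one contrast and Student for the next, the natural reading of the second is the classical interval with a pooled variance. That interval has the right width if the two groups share a variance or have equal size. With unequal sizes and unequal variances it does not. It is too narrow when the smaller group is the more variable, and too wide when the larger group is.

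The between-booster-arm intervals are the planned evidence on whether the booster works similarly after different priming vaccines. An interval that is too narrow makes priming groups look more different than the data support. One that is too wide can mask a real difference. Section 3.4.6 carries the methods of 3.4.4 into the exploratory variant analyses, so the choice spreads further.

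The 3.4.2 sentence is a separate, editorial problem: read alone, it does not tell a programmer which method applies.

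**Working it through.** **Inputs**
- Planned sizes, 18-55 years (SAP Table 1.2): Cohort 2 Pfizer-primed 515 vs 75 for each of Moderna, AstraZeneca and Janssen; Cohort 1 Pfizer-primed 215 vs 75; among B.1.351 recipients, Pfizer-primed 515 vs protein-primed 30.
- SDs on the log10 scale (SAP 3.2.1, Table 3.1): 1.0 for every booster arm; 0.65 for the naïve two-dose Comparator at D36.
- Any SD difference between two booster arms is an assumption. The SAP states none.

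**Step 1. Check that the SDs are read as the SAP uses them.** Cohort 2 Pfizer-primed non-inferiority: n = 0.97 × 515 ≈ 499 booster and 0.90 × 515 ≈ 463 Comparator. SE = √(1.0²/499 + 0.65²/463) = 0.0540. Distance to the margin = log10(1) − log10(1/1.5) = 0.1761. Ratio = 3.26. With one-sided alpha 0.025/3, power is 80.5%, as in Table 3.1. The Cohort 1 Pfizer-primed figure (208 vs 463, true ratio 1.5) comes out at 98.7%, also as stated.

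**Step 2. Coverage formula.** For groups 1 and 2:
- Pooled variance: s_p² = [(n₁−1)σ₁² + (n₂−1)σ₂²] / (n₁+n₂−2)
- SE used by the interval: SE_p = √[s_p²(1/n₁ + 1/n₂)]
- True SE: SE_t = √(σ₁²/n₁ + σ₂²/n₂)
- Approximate coverage: 2Φ(t × SE_p/SE_t) − 1, where t is the 97.5% point on n₁+n₂−2 degrees of freedom

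**Step 3. The SAP's own assumption.** With SD 1.0 in both arms, SE_p = SE_t. At 515 vs 75 both are 0.1236 and coverage is about 95%. Unequal size alone does no harm.

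**Step 4. Illustration at 515 vs 75 (t = 1.964).**
- SD 0.8 in the 515, 1.0 in the 75: s_p² = 0.6853, SE_p = 0.1023, SE_t = 0.1207, ratio 0.848, coverage 90.4%.
- SD 1.0 in the 515, 0.8 in the 75: s_p² = 0.9547, SE_p = 0.1208, SE_t = 0.1023, ratio 1.180, coverage 98.0%.
- SD 0.65 in the 515, 1.0 in the 75: SE_p = 0.0870, SE_t = 0.1190, ratio 0.731, coverage 84.9%.
- SD 1.0 in the 515, 0.65 in the 75: SE_p = 0.1190, SE_t = 0.0870, ratio 1.368, coverage 99.3%.

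**Step 5. Simulation (60,000 runs per case), pooled interval against Welch.**

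| Sizes | SDs (large, small group) | Pooled | Welch |
|---|---|---|---|
| 515 vs 75 | 1.0, 1.0 | 95.0% | 95.0% |
| 515 vs 75 | 0.8, 1.0 | 90.4% | 95.1% |
| 515 vs 75 | 1.0, 0.8 | 97.9% | 95.0% |
| 515 vs 75 | 0.65, 1.0 | 85.0% | 95.0% |
| 515 vs 75 | 1.0, 0.65 | 99.3% | 95.0% |
| 215 vs 75 | 0.8, 1.0 | 92.4% | 95.1% |
| 215 vs 75 | 1.0, 0.8 | 97.1% | 95.1% |
| 515 vs 30 | 0.8, 1.0 | 89.2% | 95.1% |
| 515 vs 30 | 1.0, 0.8 | 98.3% | 94.9% |

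At 75 vs 75 the pooled interval covers about 95% whatever the SDs.

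**Step 6. External groups.** SAP 4.3 gives neither sizes nor SDs, so no coverage figure can be calculated.

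**The case against.** The best defence is that the split follows the plan's own variance assumptions. The SAP expects unequal SDs in one place, booster (1.0) against naïve Comparator (0.65), and uses Welch there. Table 3.1 gives every booster arm an SD of 1.0, and under that assumption the Student interval is correct. Several contrasts are also balanced: Moderna, AstraZeneca and Janssen have 75 each in the 18-55 stratum and 25 each in the older stratum. Pooling is inferred rather than written, and no test, margin or decision rule hangs on these intervals.

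Most of this stands and sets the severity. It does not justify the choice of method. The single booster SD is a planning value taken from non-naïve Phase II participants at D22, not from groups primed with the vaccines now being compared, so it is weak evidence that those groups share a variance. If pooling is not intended, the estimator is unspecified and still needs a line.

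Stronger readings are tempting but unsupported:
- **That the stated 95% intervals really cover 84% to 99%.** That range needs the Comparator's SD of 0.65 to be placed on one of two booster arms, which the SAP never does.
- **That the imbalance peaks at 9:1.** The "9:1 ratio for younger adults (D614:B.1.351) and a 1:1 ratio for older adults" describes protein-primed participants (270 vs 30), who share a priming vaccine and differ in booster formulation. Across priming vaccines the planned imbalance is 515:75 (6.9:1) and, for B.1.351 recipients, 515:30 (about 17:1).
- **That the same ratios or coverage apply to the external groups.** Nothing in 4.3 supports this.
- **That the 3.4.2 sentence threatens the primary tests.** The 98.3% intervals are fixed by the printed Welch formula, and 3.4.4 restates the descriptive rule cleanly.

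**Conclusion.** The point holds as a minor one. For two sets of descriptive intervals the SAP names a method that depends on equal variances, gives no reason for it, and already contains one that does not. Under the SAP's common booster SD of 1.0 nothing is lost and coverage is about 95%. If SDs differ between priming groups, the pooled interval at the planned sizes drifts: at 515 vs 75, to roughly 90% or 98% with assumed SDs of 0.8 and 1.0, and to roughly 85% or 99% with 0.65 and 1.0. These figures are illustrations that rest on assumed SD differences and on reading Student as pooled variance. For the external groups only the choice of method can be criticised. Type I error, the powered objectives and the primary conclusions are unaffected. What is exposed is the reading of homogeneity across priming vaccines.

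**What to change.** - In 3.4.4 and 4.3, replace the Student t-distribution with the Welch t-interval, by reference to the formula in 3.4.2, for every between-group GMT or GMC ratio.
- In 3.4.2, rewrite the descriptive sentence on booster versus Comparator so that it names Welch only.
- If the sponsor prefers Student for some contrasts, state that variances are pooled and justify equal variances. The 3.4.2 sentence needs repair in either case.

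The cost is SAP wording; the Welch formula is already specified. If the variances are in fact equal, Welch loses some degrees of freedom. At 515 vs 75 with SD 1.0 in both groups, the multiplier rises from 1.964 to 1.985, an interval about 1% wider (1.985/1.964 = 1.011). At 515 vs 30 it rises from 1.964 to 2.037, about 4%.
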